3.3 Analysis populations

- The intent-to-treat (ITT) population includes all the randomized patients except those who withdrew consent. Patients who were lost to follow up will still be considered in the ITT population through imputation processes, described below.
- The per-protocol population (PP) includes all patients in the ITT population without protocol violations (mainly open-label IV milrinone infusion or

 CHU ANGERS <small>CENTRE HOSPITALIER UNIVERSITAIRE</small>	 Statistical analysis plan	N° EudraCT 2019-002145-37 CT Number : 2024-515994-83-00 SAP V1.0 Date : 15/01/2026
---	--	---

definitive stop of study medication within the first 48 hours). The protocol violations will be determined before locking the database by a group of experts.

4 Section 4 – Trial Population

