5.1 Outcome Definition

5.1.1 Primary outcome:

The primary endpoint is the proportion of good functional outcome (defined as a modified Rankin score (mRS) ≤ 2) at 3 months, obtained by centralized standardized phone interview of the patient or his/her relative.

Modified Rankin Score is rated as follow:

- 0 = No symptoms,
- 1 = No significant disability. Able to carry out all usual activities, despite some symptoms,
- 2 = Slight disability. Able to look after own affairs without assistance, but unable to carry out all previous activities,
- 3 = Moderate disability. Requires some help, but able to walk unassisted,
- 4 = Moderately severe disability. Unable to attend to own bodily needs without assistance, and unable to walk unassisted,
- 5 = Severe disability. Requires constant nursing care and attention, bedridden, incontinent,
- 6 = Death.

5.1.2 Secondary outcomes:

- a) Glasgow Outcome Scale Extended (GOSE) is obtained by centralized standardized phone interview of the patient or his/her relative done at 3 and 6 months. The GOSE is a global scale for functional outcome, categorized in 8 categories from 1 (death) to 8 (upper good recovery).
- b) EuroQOL Quality of Life Scale 5-Dimension 5-Level (EQ-5D) is a questionnaire is conducted at baseline, 3 and 6 months. It consists of a short and simple 5-part questionnaire and a visual analogue scale (VAS). It may be self-administered, completed by interview or via a proxy respondent, and is used to value and describe health states. The questionnaire data is reported as an index value - a continuous

 CHU ANGERS <small>CENTRE HOSPITALIER UNIVERSITAIRE</small>	 Statistical analysis plan	N° Eudract 2019-002145-37 CT Number : 2024-515994-83-00 SAP V1.0 Date : 15/01/2026
---	--	---

fractional outcome with boundaries between zero and one. Zero represents the worst health status and 1 the best. The EQ-VAS (visual analogue scale) is a self-administered visual scale in which respondents rate from 0 to 100 (worst and best state of health respectively) their perceived health-related quality of life at the time of response. In analyses including non-survivors, deceased patients will be given the lowest score. The EQ-5D will be analyzed as a variation from baseline at 3 and 6 months.

c) Mortality will be analyzed until 6 months.

5.1.3 Tertiary outcomes:

- a) ICU and hospital length of stays

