5.2 Analysis Methods

Unless otherwise specified, all analyses will be completed on the intention to treat population.

 CHU ANGERS <small>CENTRE HOSPITALIER UNIVERSITAIRE</small>	 Statistical analysis plan	N° EudraCT 2019-002145-37 CT Number : 2024-515994-83-00 SAP V1.0 Date : 15/01/2026
---	--	---

The characteristics at inclusion and the measures of patient assessments for each treatment arm will be described using percentages or means, standard deviations, medians and interquartile ranges, and compared using Khi-square tests or Student t tests for respectively categorical and continuous data. A summary of the proposed analyses is presented in Table 1.

5.2.1 Primary Outcome:

Primary analysis:

The main statistical analysis will be performed on the intention to treat population using a binomial logistic regression model including as covariates the treatment arm and the different stratification factors for randomization (the center, the initial WFNS score dichotomized as <3 vs ≥ 3 and the patient's consciousness at inclusion).

Secondary analysis:

As a secondary analysis, we will report absolute risk reduction using a proportional odds approach, using the Brant-Wald test at the alpha level of 5%, which may be more sensitive for detecting a shift over the entire spectrum of outcome (mRS 7-point ordinal scale).

Sensitivity analysis:

An other model will be proposed based on the ITT population, including in addition to the covariates already considered the level of consciousness and the delay before performing angiography (within 12 hours or not), and the interactions between these two covariates and the treatment arm, to assess a possible variation in the treatment effect according to the status on these two covariates

These two models will be performed on the per-protocol population as an evaluation of the robustness of their results. In any cases, the primary analysis results will be authoritative.

5.2.2 Secondary Outcomes:

- The analysis of the mRS, the extended GOS and the EQ-5D score at 3 and 6 months will be performed considering (ordinal) proportional odds models, based on the same set of covariates.
- The ICU mortality and 6 months mortality will be analyzed using Cox models based on the same set of covariates. The validation of these models will be evaluated by analyzing Schoenfeld residuals.

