 CHU ANGERS <small>CENTRE HOSPITALIER UNIVERSITAIRE</small>	 Statistical analysis plan	N° EudraCT 2019-002145-37 CT Number : 2024-515994-83-00 SAP V1.0 Date : 15/01/2026
---	--	---

5.2.3 *Tertiary outcomes*

- The analysis of angiographic successes at day 7 and 14 will be performed considering (ordinal) proportional odds models, based on the same set of covariates
- The proportion of therapeutic arteriography between each group and the median number of arteriography will be compared.
- The analysis of hospital length of stay will be carried out by using linear regression models based on the same set of covariates.
- Patients outcomes and treatment tolerance will be analyzed using logistic models for dichotomous data (transfer to a convalescent center, patients living at home at 3 and 6 months, need to initiate or to increase the catecholamine doses by 50%, occurrence of dysnatremia), or linear regression models for continuous data (DAAH90, daily dose of catecholamines, average daily urine output).

5.2.4 *Pre-planned sub-group analysis*

We plan exploratory subgroup analyses for the primary outcome (as described above) in the following sub-groups:

- Sex: female sex versus male sex. We hypothesize no treatment effect difference between male and female sex.
- Initial WFNS score <3 vs ≥ 3 . We hypothesize that the treatment effect is more important in the less severe patients (WFNS <3).
- Consciousness level at inclusion: conscious vs unconscious. We hypothesize that the treatment effect is more important in the less severe patients (conscious patients).

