mRS at 3 month	Log-binomial logistic regression with fixed effects for treatment and, and a random effect for center, initial WFNS (<3 or ≥ 3) and patient's consciousness, reported as a risk ratio with 95% CI	
 Another model adjusted with level of consciousness and delay before performing arteriography (< or \geq 12h) Sub-group analysis Per protocol analysis† Patients without missing data 	
 Proportional odds analysis using the Brant-Wald test 	
 center, initial WFNS (<3 or ≥ 3) patient's consciousness at inclusion
Secondary outcomes				
mRS at 6-months	Log-binomial logistic regression reported as a risk ratio with 95% CI		
 unadjusted model Proportional odds analysis using the Brant-Wald test 	
 center, initial WFNS (<3 or ≥ 3) patient's consciousness at inclusion
GOSE at 3 and 6 months	Linear logistic regression model, reported as mean difference with 95% CI		
 unadjusted model 	
 center, initial WFNS (<3 or ≥ 3) patient's consciousness at inclusion
EQ-5D	Linear logistic regression model, reported as mean difference with 95% CI	
 Excluding deceased patient 	
 unadjusted model 	
 center, initial WFNS (<3 or ≥ 3) patient's consciousness at inclusion
Mortality hospital	Log-binomial logistic regression reported as a risk ratio with 95% CI		
 unadjusted model 	
 center, initial WFNS (<3 or ≥ 3) patient's consciousness at inclusion
Mortality 6 months	
 Kaplan-Meier curves and Cox regression hazard ratios 		
 unadjusted model 	
 center, initial WFNS (<3 or ≥ 3) patient's consciousness at inclusion
Tertiary outcomes				
ICU and Hospital LOS	Presented as median difference with 95% CI, using quantile regression		
 median with IQR unadjusted model 	
 center, initial WFNS (<3 or ≥ 3) patient's consciousness at inclusion

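### The SAP gives two conflicting models for hospital length of stay and no rule for in-hospital deaths in either ICU or hospital stay, so the comparison depends on mortality

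*SAP*

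**What the plan says.** **Outcome.** SAP section 5.1.3 defines it only as "ICU and hospital length of stays". It gives no end point for the stay and no rule for death.

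**Model in the text.** Section 5.2.3: "The analysis of hospital length of stay will be carried out by using linear regression models based on the same set of covariates". This sentence covers hospital stay only; no model for ICU stay is named there.

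**Model in Table 1.** The row "ICU and Hospital LOS" reads "Presented as median difference with 95% CI, using quantile regression". No sensitivity analysis is listed for it.

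**Population.** Section 5.2: "Unless otherwise specified, all analyses will be completed on the intention to treat population". Section 3.3: "The intent-to-treat (ITT) population includes all the randomized patients except those who withdrew consent". Death is not a reason for leaving this population, and no exception is made for length of stay.

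**Contrast with EQ-5D.** Section 5.1.2 sets a rule: "In analyses including non-survivors, deceased patients will be given the lowest score". Table 1 adds a sensitivity analysis, "Excluding deceased patient". Length of stay has neither.

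**The concern.** There are two defects, and both can be seen in the text without any assumption.

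First, hospital stay has two main analyses that estimate different things: a difference in means in section 5.2.3 and a difference in medians in Table 1. Stay data are usually skewed, so the two can differ, and the plan does not say which one governs.

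Second, neither analysis has a death rule. A stay can end by discharge alive or by death, and a model fitted to the raw duration treats the two alike. The estimate then mixes how fast survivors leave with how many patients die and when. Mortality is a secondary outcome of this trial, so a difference in deaths is one of the effects being looked for. If one occurs, the length-of-stay estimate could be read as a cost or a benefit of milrinone when it only reflects who survived long enough to have a full stay.

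**Working it through.** **1. The plan's own figure.** The SAP gives no expected stay, mortality rate or time of death, so there is no figure to reproduce. The numbers below illustrate the mechanism and are not forecasts.

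**2. The two instructions side by side**

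| | Section 5.2.3 | Table 1 |
|---|---|---|
| Hospital stay | linear regression (mean difference) | quantile regression (median difference) |
| ICU stay | not mentioned | quantile regression (median difference) |
| Rule for death | none | none |
| Sensitivity analysis | none | none |

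**3. Assumed inputs.** Survivor stay: gamma, shape 3, scale 10, mean 30 days. Stay ending in death: gamma, shape 2, scale 6, mean 12 days. Both distributions are the same in the two arms, so treatment has no effect on stay; only mortality differs.

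**4. Mean.** With mortality p, the all-patient mean is 30(1 − p) + 12p = 30 − 18p. The difference, lower-mortality arm minus the other, is 18 × (difference in mortality).

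- 20% versus 12%: 27.84 − 26.40 = 18 × 0.08 = +1.44 days.
- 25% versus 15%: 27.30 − 25.50 = 18 × 0.10 = +1.80 days.

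**5. Median.** Solve p·F_death(m) + (1 − p)·F_survivor(m) = 0.5 for m in each arm.

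- 20% versus 12%: 24.51 − 22.91 = +1.60 days.
- 25% versus 15%: 23.92 − 21.87 = +2.05 days.

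The median moves at least as much as the mean, so settling the model conflict in favour of either model leaves the problem in place.

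**6. Dependence on the timing of death.** In general the mean shift is (survivor mean − mean time to death) × (difference in mortality). It is zero when the two times are equal and negative when deaths come later. A separate simulation with lognormal stays (coefficient of variation 0.6, survivor median 30 days, 2,000,000 patients per arm, again no effect on stay) gives, as mean (median) shift in days:

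| Median time to death | 25% vs 15% | 20% vs 15% | 15% vs 10% |
|---|---|---|---|
| 8 days | +2.6 (+2.7) | +1.3 (+1.3) | +1.2 (+1.1) |
| 12 days | +2.1 (+2.2) | +1.0 (+1.1) | +1.0 (+1.1) |
| 20 days | +1.2 (+1.2) | +0.6 (+0.6) | +0.6 (+0.5) |
| 30 days | 0 (0) | 0 (0) | 0 (0) |
| 35 days | −0.6 (−0.5) | −0.3 (−0.3) | −0.3 (−0.3) |

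**7. Size against precision.** Take the gamma inputs, 180 patients per arm (360 planned, 1:1) and no covariate adjustment. For 20% versus 12% mortality the all-patient variances are 306.2 and 306.9, so the 95% half-width for the mean difference is 1.96 × √((306.2 + 306.9)/180) = 3.6 days. For the median difference the large-sample half-width is about 4.3 days. The shifts in steps 4 and 5 are at most about half of these.

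**The case against.** The strongest reply has four parts.

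- **The plan is silent on deaths.** A reader might infer that the SAP scores deaths as short, favourable stays. It states no such rule. That a stay ends at death follows from the intention-to-treat default and the lack of any exception, and an operational definition could sit in the protocol, which is not shown. This limits the wording of the point but does not remove it: the SAP sets the death rule for EQ-5D itself, so the matter belongs in this document.
- **The direction is not fixed.** A reader might also infer that a life-saving arm must appear to lengthen stay. That holds only if deaths come earlier than survivors' discharge, and the SAP has no data on this. The objection stands as to sign. The estimate still depends on mortality unless the two timings match.
- **Raw stay is a legitimate measure of bed use.** This stands. The SAP does not label length of stay as a measure of clinical benefit, and the estimate misleads only if it is read as one.
- **Other outcomes cover the gap.** Mortality is reported to 6 months, and the days-alive-and-at-home outcome (DAAH90) accounts for death. Section 3.1 reserves p-values for primary and secondary outcomes. All of this lowers the stakes. But DAAH90 measures time at home, not ICU or hospital use, and it does not correct a length-of-stay estimate that will still be reported with a confidence interval.

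**Conclusion.** The point holds in this form. Section 5.2.3 and Table 1 contradict each other on the model for hospital stay, ICU stay has a model only in Table 1, and neither place says how deaths enter. Followed as written, the plan gives a treatment difference that depends on mortality as well as on speed of discharge, under either model.

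The size can only be illustrated. With survivors staying a mean of 30 days, deaths at mean day 12 and no effect on stay, the artefact is +1.4 days (mean) or +1.6 (median) for mortality of 20% versus 12%, and +1.8 or +2.0 for 25% versus 15%. These shifts are small beside the likely confidence interval, and their sign depends on when deaths occur. Because the outcome is tertiary and has no p-value, this is a desirable correction. It does not threaten the trial's main conclusions.

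**What to change.** Before database lock, amend section 5.1.3, section 5.2.3 and Table 1 so that ICU and hospital stay share one model and one explicit death rule. Either of these would do:

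- time to discharge alive (from ICU, from hospital), with death as a competing event; or
- days alive and out of ICU, and days alive and out of hospital, to day 90, with deaths scored 0.

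Keep raw length of stay, shown by arm and vital status, as description only. A survivors-only comparison should not become the main analysis, because the survivors of the two arms need not be comparable if mortality differs.

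The cost is SAP wording. Stay and mortality are already trial outcomes, so no new data should be needed. The downsides are a measure less familiar than raw length of stay and, for the day-90 version, partial overlap with DAAH90.

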5.3 Missing Data

First, every attempt will be made to retrieve the missing data. All missing data will be reported and the frequencies of these will be calculated.

A description of the patients characteristics depending on whether they have missing data or not will be proposed to distinguish missing completely at random or missing at random data.

 CHU ANGERS <small>CENTRE HOSPITALIER UNIVERSITAIRE</small>	 Statistical analysis plan	N° EudraCT 2019-002145-37 CT Number : 2024-515994-83-00 SAP V1.0 Date : 15/01/2026
---	--	---

In case of missing data, multiple imputations will be performed considering chained equations with fully conditional specification. The considered covariates included in this imputation process will include all covariates observed at the end-point evaluation (including the treatment allocation). Ten imputations will be performed for each missing data. This analysis will allow to calculate the Fraction of Missing Information (FMI), and then the Relative Efficiency (RE). If the RE ≥ 0.99 , then the number of imputations will be considered as appropriate. If not, the number of imputations will be determined as greater than the FMI value * 100 to ensure high relative efficiency.

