2.3 Sample Size

We estimated that the rate of favorable neurological outcomes (defined as a mRS ≤ 2) at 3 months in patients with vasospasm following acute aSAH without milrinone infusion is approximately 35%. (This percentage was estimated based on the analysis of data extracted from the ATLANREA database, including 436 patients in 3 years, ClinicalTrials.gov - identifiant : NCT02714387) The proportion of favorable outcomes reported in case series of patients with vasospasm treated with milrinone is between 50 and 60%. For our sample size calculation, we thus hypothesized a percentage of favorable outcomes at 3 months of 35 and 50% respectively in the control and milrinone group. Considering a two sided test and a type I and type II error rates of 5 and 20%, the sample size required is 340 (170 patients in each group). Considering a 5% proportion of withdrawals, we planned to include 360 patients, and increased this number to 370 to compensate for patients included but not randomized because of early withdrawal.

 CHU ANGERS <small>CENTRE HOSPITALIER UNIVERSITAIRE</small>	 Statistical analysis plan	N° Eudract 2019-002145-37 CT Number : 2024-515994-83-00 SAP V1.0 Date : 15/01/2026
---	--	---

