3.1 Confidence Intervals and P-values

The statistical uncertainty of all estimates will be expressed as two-sided 95% confidence intervals. A p-value will only be reported for all the primary and secondary outcomes. A p-value <0.05 will be considered significant.

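### The ten-imputation rule with its 0.99 relative-efficiency check allows Monte Carlo error of about a tenth of the standard error in the primary estimate: a minor weakness, cheaply removed

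*SAP*

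**What the plan says.** Section 5.3 (Missing Data) prescribes multiple imputation by chained equations: "Ten imputations will be performed for each missing data". The FMI and RE are then calculated. If RE is at least 0.99, "then the number of imputations will be considered as appropriate". The other branch reads: "If not, the number of imputations will be determined as greater than the FMI value * 100 to ensure high relative efficiency". Section 5.3 names no random seed and sets no limit on Monte Carlo error.

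The imputation feeds the primary result. Section 3.3 states: "Patients who were lost to follow up will still be considered in the ITT population through imputation processes". Section 5.2.1 runs the primary model on that population, and Table 1 lists the analysis of patients without missing data only as a sensitivity analysis. Section 3.1 sets the decision rule: "A p-value <0.05 will be considered significant".

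**The concern.** RE compares the variance of the point estimate from m imputations with the variance from infinitely many. An RE of 0.99 means that about 1% of efficiency is lost. It does not say how far the estimate and its p-value would move if the same data were imputed again with another seed. That movement scales with the square root of FMI/m, so a 1% variance loss corresponds to a shift of about 10% of a standard error.

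The primary conclusion is judged against a fixed threshold. Two analysts who follow section 5.3 exactly, with different seeds, could therefore report opposite verdicts when the result is close to 0.05. With no seed specified, the SAP does not determine which of the two is the trial's result.

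**Working it through.** **Inputs from the SAP.** m = 10, RE ≥ 0.99, and m > 100 × FMI otherwise (5.3); two-sided p < 0.05 (3.1); design rates "35 and 50% respectively in the control and milrinone group" (2.3).

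**Assumption.** The SAP gives no FMI and no missing-mRS rate; section 4.2 expects few such events. I use FMI = 0.025, 0.05 and 0.101, the last being the most that the RE check accepts.

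**1. The plan's own figure.** Section 2.3: "Considering a two sided test and a type I and type II error rates of 5 and 20%, the sample size required is 340". The usual two-proportion formula (pooled variance under the null) gives 169.3, so 170 per group and 340 in total. The figure is reproduced. At 80% power the test statistic is centred at 1.960 + 0.842 = 2.802.

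**2. What the RE check accepts.** RE = 1/(1 + FMI/m). With m = 10, RE ≥ 0.99 means FMI ≤ 10 × (1/0.99 − 1) = 0.101.

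**3. Monte Carlo error as a share of the SE**, s = √(FMI/m):
- FMI 0.025, m = 10: √0.0025 = 0.050
- FMI 0.05, m = 10: √0.005 = 0.071
- FMI 0.101, m = 10: √0.0101 = 0.1005

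**4. The second branch.** The smallest whole m above 100 × FMI:
- FMI 0.15, m = 16: 0.097
- FMI 0.20, m = 21: 0.098
- FMI 0.30, m = 31: 0.098

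The ceiling is again about 0.10.

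**5. Borderline results.** Let z be the statistic from infinitely many imputations. By normal approximation the share of seeds on the other side of 0.05 is Φ(−|z − 1.960|/s). A limiting p of 0.045 has z = 2.005 and a limiting p of 0.055 has z = 1.919.

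| FMI | m = 10: p 0.045 / 0.055 | m = 100: p 0.045 / 0.055 |
|---|---|---|
| 0.025 | 19% / 21% | 0.2% / 0.5% |
| 0.05 | 26% / 28% | 2% / 3% |
| 0.101 | 33% / 34% | 8% / 10% |

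A simulation of Rubin pooling (40,000 replicates per setting), which also lets the between-imputation variance vary, gave 20 to 39% for m = 10 and 0.3 to 11% for m = 100. As the limiting p approaches 0.05, crossing tends to one half for any m.

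**6. All trials under the design effect.** Averaging step 5 over z ~ N(2.802, 1) gives approximately φ(0.842) × √(2/π) × s = 0.280 × 0.798 × s = 0.223 s. This is the chance that the verdict differs from that of infinitely many imputations:
- m = 10: 1.1% (FMI 0.025), 1.6% (0.05), 2.2% (0.101)
- m = 100: 0.4%, 0.5%, 0.7%

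Two seeds disagree with each other √2 times as often: 1.6%, 2.2% and 3.2% at m = 10. Numerical integration gives the same values.

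**7. Noise in the check.** The FMI is itself estimated from ten imputations. In simulation, a true FMI of 0.15 passed the RE check in about 18% of runs, with an error of √(0.15/10) = 0.12 SE. The 0.10 ceiling is therefore approximate.

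**The case against.** The best defence is that the rule is a deliberate, data-driven choice that holds the efficiency loss to about 1%, and that the practical risk is small. That stands: no estimate is biased, no figure in the SAP is false, and step 6 shows a changed verdict in only one or two trials in a hundred.

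A reader might infer from step 5 that the trial's conclusion commonly hangs on the seed. The document does not support this. Those percentages apply only if the limiting p happens to lie very near 0.05.

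A reader might also take the 5% in section 2.3 as the expected share of missing mRS. It is an allowance for withdrawals. Section 3.3 removes patients who withdrew consent from the ITT population, although section 4.2 keeps their inclusion data for imputation, so the text is mixed. Section 5.1.1 lets a relative answer the telephone interview and section 5.3 promises every attempt at retrieval. The FMI may therefore be at the low end of the range, and with no missing outcomes the issue disappears.

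Two further defences carry less weight. The complete-case analysis in Table 1 does not depend on a seed, but it does not replace the primary p-value. Section 2.4 delays unblinding until the primary and secondary analyses are complete, which prevents a seed being chosen in knowledge of the arms. It does not make the p-value stable, and a p-value can be seen with coded arms.

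**Conclusion.** The point holds as a minor one. Both branches of section 5.3 allow Monte Carlo error of up to about 0.10 SE in the primary estimate, because the criterion controls efficiency and not repeatability. For an assumed FMI of 0.025 to 0.101, the expected harm is a changed verdict in about 1.1 to 2.2% of trials under the 35% versus 50% design. In a borderline trial the dependence on the seed is material, at about 19 to 34% of seeds for a limiting p of 0.045 or 0.055. These figures rest on the assumed FMI range, on the normal approximation and, for the percentage of trials, on the design effect being true. This is avoidable imprecision in the specification, not an error that threatens the trial's validity.

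**What to change.** In section 5.3, replace the ten-imputation and RE rule with at least 100 imputations for the primary and all other imputed analyses, and record the random seed before database lock. Add that m is raised if the Monte Carlo standard error of the pooled log effect exceeds 3% of its standard error.

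The 100 must be a minimum. At FMI 0.101 it gives √(0.101/100) = 0.032, just above the 3% limit, and about 0.101/0.03² = 112 imputations are needed. At FMI 0.05 about 56 would do. The 100 and the 3% are working choices; the SAP does not supply them. A seed alone would make the result reproducible but still arbitrary; the larger m removes most of the arbitrariness.

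The cost is two or three sentences in the SAP and a little more computing time. The model, the population and the data collection do not change.
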